## Annex 3 – Field trial protocols

SENIOR	WITH	MILD	COGNITIV	F IN	JPAIR	MENT
SENIOR			COGINITIV	E 11	VII / \II \	

#### RECRUITMENT PROTOCOL

Subject Identification code:// Date of compilation:// Country of compilation: Name of the interviewer:						
SOCIO-DEMOGRAPHIC QUESTIONNA	IRE					
Date of birth (dd /mm /yyyy)/						
12. Gender: 🗆 male	🗆 female	🗆 dive	erse			
13. Residence:	🗆 Suburban		Rural community			
14. Housing situation:	□ Alone		Shared apartment			
With (marriage) partner	🗆 Family		□ Other:			
15. Marital status:	Single		□ widowed			

 
married / registered civil
 
partnership
 
	partnership	□ divo	orced 🗆 solid			
16. Do you have children?	□ no	🗆 yes	ightarrow if yes, how much:			
17. Do you have grandchildren	!? □ no	□ yes	ightarrow if yes, how much:			
18. Highest level of education:	🗆 No school	degree	High school			
□ Secondary school □ Spe	ecialized baccal	aureate	Junior high school			

□ University degree □ Other: \_\_\_\_\_

- 19. Are you currently employed? $\Box$  no $\Box$  yes $\rightarrow$  if yes, pleasemark where applicable: $\Box$  Full-Time $\Box$  Part-Time $\Box$  Minijob
- 20. Are you currently retired?  $\Box$  no  $\Box$  yes  $\rightarrow$  if yes, since when:\_\_\_\_\_ (Year)
- 21. Which of the following devices do you use frequently (more than once a week)? (multiple answers possible) □ Computer □ Tablet □ Smartphone □ None
- 22. How would you rate your experience using these devices (e.g., video calling, emailing, WhatsApp) on a scale of 1 (no experience) to 5 (a lot of experience)?
  Very little experience 
  Little experience 
  Not a little/not a lot 
  Somewhat 
  Very much
- 23. No acute or untreated medical problems; severe autonomic system dysfunction; severe behavioral syndromes not compensated by medication; concomitant neurological diseases; severe systemic diseases with life expectancy < 1 year; diagnosed dementia or other neurodegenerative diseases; diagnosed psychiatric diseases □ no □ yes

Clinical Frailty Scale score:
MOCA score:
GDS score:
MAC-Q score :

#### MONTREAL COGNITIVE ASSESSMENT (MOCA)

#### **REISEBERG SCALE**

Level	Clinical characteristics
1 No cognitive decline	No subjective complaints of memory deficit. No memory deficit evident on clinical interview.
2 Very mild cognitive decline (Age Associated Memory Impairment)	Subjective complaints of memory deficit, most frequently in following areas: (a) forgetting where one has placed familiar objects; (b) forgetting names one formerly knew well. No objective evidence of memory deficit on clinical interview. No objective deficits in employment or social situations. Appropriate concern with respect to symptomatology.
3 Mild cognitive decline (Mild Cognitive Impairment)	Earliest clear-cut deficits. Manifestations in more than one of the following areas: (a) patient may have gotten lost when traveling to an unfamiliar location; (b) coworkers become aware of patient's relatively poor performance; (c) word and name finding deficit becomes evident to intimates; (d) patient may read a passage or a book and retain relatively little material; (e) patient may demonstrate decreased facility in remembering names upon introduction to new people; (f) patient may have lost or misplaced an object of value; (g) concentration deficit may be evident on clinical testing. Objective evidence of memory deficit obtained only with an intensive interview. Decreased performance in demanding employment and social settings. Denial begins to become manifest in patient. Mild to moderate anxiety accompanies symptoms.
4 Moderate cognitive decline (Mild Dementia)	Clear-cut deficit on careful clinical interview. Deficit manifest in following areas: (a) decreased knowledge of current and recent events; (b) may exhibit some deficit in memory of ones personal history; (c) concentration deficit elicited on serial subtractions; (d) decreased ability to travel, handle finances, etc. Frequently no deficit in following areas: (a) orientation to time and place; (b) recognition of familiar persons and faces; (c) ability to travel to familiar locations. Inability to perform complex tasks. Denial is dominant defense mechanism. Flattening of affect and withdrawal from challenging situations frequently occur.
5 Moderately severe cognitive decline (Moderate Dementia)	Patient can no longer survive without some assistance. Patient is unable during interview to recall a major relevant aspect of their current lives, e.g., an address or telephone number of many years, the names of close family members (such as grandchildren), the name of the high school or college from which they graduated. Frequently some disorientation to time (date, day of week, season, etc.) or to place. An educated person may have difficulty counting back from 40 by 4s or from 20 by 2s. Persons at this stage retain knowledge of many major facts regarding themselves and others. They invariably know their own names and generally know their spouses' and children's names. They require no assistance with toileting and eating, but may have some difficulty choosing the proper clothing to wear.

6 Severe cognitive	May occasionally forget the name of the spouse upon whom they are
decline (Moderately	entirely dependent for survival. Will be largely unaware of all recent events
Severe Dementia)	and experiences in their lives. Retain some knowledge of their past lives but
	this is very sketchy. Generally unaware of their surroundings, the year, the
	season, etc. May have difficulty counting from 10, both backward and,
	sometimes, forward. Will require some assistance with activities of daily
	living, e.g., may become incontinent, will require travel assistance but
	occasionally will be able to travel to familiar locations. Diurnal rhythm
	frequently disturbed. Almost always recall their own name. Frequently
	continue to be able to distinguish familiar from unfamiliar persons in their
	environment. Personality and emotional changes occur. These are quite
	variable and include: (a) delusional behavior, e.g., patients may accuse their
	spouse of being an impostor, may talk to imaginary figures in the
	environment, or to their own reflection in the mirror; (b) obsessive
	symptoms, e.g., person may continually repeat simple cleaning activities; (c)
	anxiety symptoms, agitation, and even previously nonexistent violent
	behavior may occur; (d) cognitive abulla, i.e., loss of willpower because an
	individual cannot carry a thought long enough to determine a purposeful
	course of action.
7 Very severe	All verbal abilities are lost over the course of this stage. Frequently there is
cognitive decline	no speech at all -only unintelligible utterances and rare emergence of
(Severe Dementia)	seemingly forgotten words and phrases. Incontinent of urine, requires
	assistance toileting and feeding. Basic psychomotor skills, e.g., ability to
	walk, are lost with the progression of this stage. The brain appears to no
	longer be able to tell the body what to do. Generalized rigidity and
	developmental neurologic reflexes are frequently present.

#### 4-ITEMS GERIATRIC DEPRESSION SCALE (GDS)

Questions	Circle answ	e One er	Score
Are you basically satisfied with your life?	yes	NO	
Do you feel that your life is empty?	YES	no	
Are you afraid that something bad is going to happen to you?	YES	no	
Do you feel happy most of the time?	yes	NO	

#### Geriatric Depression Scale (GDS-4)

The 4 item Geriatric Depression Scale is easy and quick to perform with a high sensitivity and specificity.

GDS-4 is of limited clinical value in monitoring the severity of the depressive episode but more useful in excluding depression. If depression is indicated then use the GDS-15 scale.

Care must be taken as dementia and depression often co-exist.

To Score: If answer chosen is in CAPITALS then give 1 mark otherwise 0

- Results: 0 = Not Depressed 1 = Uncertain 2 to 4 = Depressed

#### MEMORY ASSESSMENT CLINICS-QUESTIONNAIRE (MAC-Q)

As compared to when you were in high school or college, how would you describe your ability to perform the following tasks involving your memory?

Activities	Much better now	Somewhat better now	About the same	Somewhat poorer now	Much poorer now
Remembering the name of a person just introduced to you	1	2	3	4	5
Recalling telephone numbers or zip codes that you use on a daily or weekly basis	1	2	3	4	5
Recalling where you put objects (such as keys) in your home or office	1	2	3	4	5
Remembering specific facts from a newspaper or magazine article you have just finished reading	1	2	3	4	5
Remembering the item(s) you intend to buy when you arrive at the grocery store or pharmacy	1	2	3	4	5
In general, how would you describe your memory compared to the past?	2	4	6	8	10

**Total score** 

#### **CLINICAL FRAILTY TEST**

1	Ì	Very Fit - People who are robust, active, energetic and motivated. These people commonly exercise regularly. They are among the fittest for their age.
2	Ţ	Well - People who have no active disease symptoms but are less fit than category 1. Often, they exercise or are very active occasionally, e.g. seasonally.
3	Ì	Managing Well - People whose medical problems are well controlled, but are not regularly active beyond routine walking.
4	A	Vulnerable - While not dependent on others for daily help, often symptoms limit activities. A common complaint is being "slowed up", and/or being tired during the day.
5		Mildly Frail - These people often have more evident slowing, and need help in high order IADLs (finances, transportation, heavy housework, medications). Typically, mild frailty progressively impairs shopping and walking outside alone, meal preparation and house work.
6		Moderately Frail - People need help with all outside activities and with keeping house. Inside, they often have problems with stairs and need help with bathing and might need minimal assistance (cuing, standby) with dressing.
7	A.	Severely Frail - Completely dependent for personal care, from whatever cause (physical or cognitive). Even so, they seem stable and not at high risk of dying (within $\sim 6$ months).
8		Very Severely Frail - Completely dependent, approaching the end of life. Typically, they could not recover even from a minor illness.
9	6	Terminally III - Approaching the end of life. This category applies to people with a life expectancy < 6 months, who are not otherwise evidently frail.

#### TO – BEFORE THE TREATMENT

Subject Identification code: \_\_\_/\_\_\_/\_\_\_ Date of compilation: \_\_\_\_\_/\_\_\_\_/\_\_\_\_/ Country of compilation: \_\_\_\_\_

Name of the interviewer: \_\_\_\_\_

#### UCLA SCALE . . . . .

Statement	Never	Rarely	Sometimes	Often
I feel in tune with the people around me	1			
Llack companionship	1	2	3	4
There is no one I can turn to	1	2	3	4
l do not feel alone a	1	2	3	4
l feel part of a group of friends a	1	2	3	-4
[ have a lot in common with the people around me a	1	2	.3	Ļ
l am no longer close to anyone	1	2	3	4
My interests and ideas are not shared by those				
around me	1	2	3	4
am an outgoing person a	1	2	3	4
There are people I feel close to a	1	2	3	4
feel left out	1	2	3	4
My social relationships are superficial	1	2	3	-1
No one really knows me well	1	2	3	4
I feel isolated from others	1	2	3	+
I can find companionship when I want it a	1	2	3	4
There are people who really understand men	1	2	3	4
am unhappy being so withdrawn	1	2	3	4
People are around me but not with me	1	2	3	4
There are people I can talk to a	1	2	3	4
There are people I can turn to a	1	2	3	4

. The total score is the sum of all 20 items. In should be represent (i.e., 1 = 4, 2, -3, 3 = 2, 4 = 1) before corring.

#### WARWICK-EDINBURH MENTAL WELLBEING SCALE (WEMWBS)

STATEMENTS	None of the time	Rarely	Some of the time	Often	All of the time
1. I've been feeling optimistic about the future	1	2	3	4	5
2. I've been feeling useful	1	2	3	4	5
3. I've been feeling relaxed	1	2	3	4	5
4. I've been feeling interested in other people	1	2	3	4	5
5. I've had energy to spare	1	2	3	4	5
6. I've been dealing with problems well	1	2	3	4	5
7. I've been thinking clearly	1	2	3	4	5
8. I've been feeling good about myself	1	2	3	4	5
9. I've been feeling close to other people	1	2	3	4	5
10. I've been feeling confident	1	2	3	4	5
11. I've been able to make up my own mind about things	1	2	3	4	5
12. I've been feeling loved	1	2	3	4	5
13. I've been interested in new things	1	2	3	4	5
14. I've been feeling cheerful	1	2	3	4	5

Below are some statements about feelings and thoughts. Please tick the box that best describes your experience of each over the last 2 weeks.

"Warwick-Edinburgh Mental Wellbeing Scale (WEMWBS). "NHS Health Scotland, University of Warwick and University of Edinburgh, 2006, all rights reserved."

#### EQ-5D-5L

Under each heading, please tick the ONE box that best describes your health TODAY

MOBILITY	
I have no problems in walking about	
I have slight problems in walking about	
I have moderate problems in walking about	
I have severe problems in walking about	
I am unable to walk about	
SELF-CARE	_
I have no problems washing or dressing myself	
I have slight problems washing or dressing myself	
I have moderate problems washing or dressing myself	
I have severe problems washing or dressing myself	
I am unable to wash or dress myself	
USUAL ACTIVITIES (e.g. work, study, housework, family or leisure activities)	
I have no problems doing my usual activities	
I have slight problems doing my usual activities	
I have moderate problems doing my usual activities	
I have severe problems doing my usual activities	
I am unable to do my usual activities	
PAIN / DISCOMFORT	_
I have no pain or discomfort	
I have slight pain or discomfort	
I have moderate pain or discomfort	
I have severe pain or discomfort	
I have extreme pain or discomfort	
ANXIETY / DEPRESSION	_
I am not anxious or depressed	
I am slightly anxious or depressed	
I am moderately anxious or depressed	
I am severely anxious or depressed	
I am extremely anxious or depressed	

#### QUALITY OF LIFE – ALZHEIMER'S DISEASE (QOL-AD)

#### T2 – AFTER SIX MONTHS

Subject Identification code: \_\_\_/\_\_\_/\_\_\_

Country of compilation: \_\_\_\_\_

Name of the interviewer: \_\_\_\_\_

#### MONTREAL COGNITIVE ASSESSMENT (MOCA)

MEMORY ASSESSMENT CLINICS-QUESTIONNAIRE (MAC-Q)

As compared to when you were in high school or college, how would you describe your ability to perform the following tasks involving your memory?

Activities	Much better now	Somewhat better now	About the same	Somewhat poorer now	Much poorer now
Remembering the name of a person just introduced to you	1	2	3	4	5
Recalling telephone numbers or zip codes that you use on a daily or weekly basis	1	2	3	4	5
Recalling where you put objects (such as keys) in your home or office	1	2	3	4	5
Remembering specific facts from a newspaper or magazine article you have just finished reading	1	2	3	4	5
Remembering the item(s) you intend to buy when you arrive at the grocery store or pharmacy	1	2	3	4	5
In general, how would you describe your memory compared to the past?	2	4	6	8	10

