## 3 Field trial

#### 3.1 Study design

The field trial will be conducted as a controlled longitudinal study, with a before and after design where the observations are made on a series of enrolled individuals, receiving the intervention described below with control group, with data collected before and after the installation and use of the technical solution. The goal of trial evaluation is to assess the engAGE technology integration into everyday life, effectiveness on mitigating the cognitive decline, acceptance over six months, security and reliability of proposed solutions as well as the business perspective reflecting the market demand (including the willingness to pay) for the developed services. The field trial procedure will be divided into two different phases, after the recruitment of the participants: Baseline evaluation (T0, M1) and Final evaluation (T1, M6), with the aim of collecting data as follows:

- **Recruitment phase** (R): the recruitment protocol will include general information on the subjects, in particular, health status and cognitive condition. The information will be collected with the help of the caregiver/family member if needed.
- **Baseline evaluation** (T0, M1): that will consist of the first real contact with the users and their families, before the start of the field trial.
- **Mid-term evaluation** (T1, M3): the aim of mid-term evaluation is to collect useful information on the use of the engAGE platform after a short period of use for detecting and analysing the technology acceptance and usability issues.
- Final evaluation (T2, after six months of use, M6): the aim of this phase is to collect useful information on the whole benefits perceived by the users after a meaningful period of use of the system. The final evaluation will be conducted after the system de-installation, to detect and analyse the impact of the system in the daily life of the older people and their family. Moreover, the final evaluation aims to gain knowledge on elderly technology acceptance and usability issues to be compared with mid-term results (T1), in order to assess the longterm acceptance and provide methodological approach for further studies in the field.

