#### 3.2.4 Inclusion criteria

- PRIMARY END USERS (SMCI):
  - over 65 years old;
  - MoCA score 21 25;
  - MAC-Q ≥ 25;
  - Reisberg scale 2 4;
  - Clinical Frailty Scale score 1 3;
  - 4-items GDS score  $\leq$  1.
- SECONDARY END USERS (INFORMAL CAREGIVERS):
  - Over 18 years old;
  - Primary informal caregiver of the user (see the user at least 2 times per week);

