#### 3.4 Outcomes

In this section the outcomes measured throughout the field trials are reported. The main focus of the engAGE project, and so of the field trial, is the perceived stability of cognitive capabilities of people with MCI. In second place, the acceptance and the usability of the platform, as well as the caregivers' benefits have to be assessed. Thus, the outcomes are the following:

- PRIMARY END USERS (SMCI):
  - Primary outcome: perceived stability of cognitive status (MAC-Q)

- Secondary outcomes: Adherence to intervention, wellbeing, quality of life, acceptance and usability, cost-benefit analysis
- SECONDARY END USERS (INFORMAL CAREGIVERS):
  - Reduction/stability of informal caregiver's burden
  - Improvement of well-being, psychological status
  - Acceptability, usability and affordability of the solution
- TERTIARY END USERS (FORMAL CAREGIVERS):
  - Improving quality of work.

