The **Reisberg Scale** [2] consists of 7 major clinical stages. It is used by clinicians and in care settings, but may be especially helpful for caregivers, as it is noticeably detailed regarding the general abilities of an individual at each stage and provides information about what to expect at different stages. The scores go from no cognitive decline (1) to very severe cognitive decline (7), through stages 2, 3, and 4 that are respectively: Very mild cognitive decline (age-associated memory impairment), mild cognitive impairment, and moderate cognitive decline.

The **4-items Geriatric Depression Scale (GDS)** [3] is a 4-items scale whose answers are yes or no. If all the items are answered negatively then the depression is excluded; if only one item is answered positively then the situation is uncertain; if at least 2 items are answered positively, the patient is depressed. Thus, this scale is easy and quick, and very useful in excluding depression.

The **Memory Assessment Clinics – Questionnaire (MAC-Q)** [4] is a 6-item scale that uses a 5-item Likert scale from "much better now"=1 to "much worse now"=5, and the last question scores double. The questionnaire asks the person to compare his or her memory with a previous period to measure age-related memory decline. Five items address specific situations frequently reported as problematic by those who experience memory loss with age. One item is a global item assessing general memory decline. A cutoff of 25 points or more indicates that the individual has a memory disorder.

**Clinical Frailty Scale (CFS).** [5] This descriptive scale divides the older participants into 9 classes based on the information provided by them and their relatives: between 1 and 3 the patient is non-frail, pre-frail if 4, he is frail from 5 to 9.

The **UCLA scale** [10] is a 20-item scale designed to measure one's subjective feelings of loneliness as well as feelings of social isolation. Participants rate each item as either O ("I often feel this way"), S ("I sometimes feel this way"), R ("I rarely feel this way"), N ("I never feel this way").

**EQ Visual Analogue Scale (EQ VAS)** [11] records the respondent's self-rated health on a 20 cm vertical, visual analogue scale with end-points labelled 'the best health you can imagine' and 'the worst health you can imagine'. This information can be used as a quantitative measure of health as judged by the individual respondents.

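### The primary outcome (MAC-Q) never asks about change since study entry, so an unchanged or slightly better score within the experimental group cannot be read as six-month stability or as an effect

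*Combined protocol and SAP*

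**What the plan says.** Section 3.4 defines, for the seniors: "Primary outcome: perceived stability of cognitive status (MAC-Q". Table 5 in section 3.5 schedules the MAC-Q at recruitment (R) and at T2 only. Section 3.2.4 also makes a score of 25 or more an entry criterion, so the R score both selects the participant and serves as baseline.

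The forms in Annex 3 are the same at R and T2. The stem opens "As compared to when you were in high school or college, how would you describe your ability", and is followed by five memory tasks with five response options each. The sixth item, which counts double, reads "In general, how would you describe your memory compared to the past". Section 3.5 describes the scale in the same spirit: it "asks the person to compare his or her memory with a previous period to measure age-related memory decline".

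Section 3.1 lists among the goals "effectiveness on mitigating the cognitive decline, acceptance over six months". The six months there qualify acceptance; for the MAC-Q the period follows from T2 being held after six months of use. Section 3.7 asks under its first hypothesis whether cognitive status improves, and plans two MAC-Q comparisons: between EG and control group (CG), and before versus after within EG. Section 4.1 describes pre/post tests in general and, for the MAC-Q, subscales, summaries and correlations. It names no between-arm test, and neither 3.4 nor 4.1 gives a margin or responder rule for stability.

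**The concern.** The outcome is stability over the trial, but the form asks about a reference point decades before it. Someone who felt somewhat poorer than at school on entry may give the same answer six months later whether memory has since improved, held or slipped a little. Other instruments in the senior's booklet state a recent window (the last two weeks for the WEMWBS, today for the EQ-5D-5L); the primary outcome does not. I found no T2 question asking the senior whether memory has changed since joining.

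The intra-group comparison in section 3.7 is therefore exposed. With no margin stated, a flat EG score could be reported as the primary outcome achieved, and a small fall in score as improvement, although either can arise with no effect of the system.

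**Working it through.** **The plan's own figure.** The only size stated is 80 randomised (section 3.1). Table 2 gives EG 20+20+8 = 48 to 22+23+10 = 55, plus at least 30 controls: 78 to 85 at the minimum control size, which contains 80. It cannot be reproduced from a power formula, because alpha, power, SD and effect size are not given.

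**1. Scale.** Five items score 1–5 and the sixth 2–10 (Annex 3).
- Minimum 5×1 + 2 = 7; maximum 5×5 + 10 = 35; all answers at the middle option 5×3 + 6 = 21.
- The sixth item carries up to 10/35 = 28.6% of the maximum.
- Higher is worse. A person entering at 25 can worsen by 35 − 25 = 10 points or improve by 25 − 7 = 18.

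**2. Remoteness of the anchor.** Participants are "over 65 years old". If school or college ended at 18–22 (assumption), the comparison reaches back at least 65 − 22 = 43 to 65 − 18 = 47 years. Six months is 0.5/43 = 1.2% to 0.5/47 = 1.1% of that. This describes how distant the anchor is; it does not measure responsiveness.

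**3. What EG alone would show with no true change.** The documents give no MAC-Q mean, SD or retest correlation, so these are assumed: mean μ 23–27, SD σ 4–5, retest correlation r 0.6–0.9. Scores at R and T2 were drawn from a bivariate normal with the same mean and SD at both visits, rounded, clipped to 7–35, and kept if the R score was 25 or more (24 settings, 400,000 draws each).

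| Quantity under zero true change | Range over settings |
|---|---|
| Mean change, T2 minus R | −0.2 to −2.0 (apparent improvement) |
| Not worse (change ≤ 0) | 64% to 75% |
| Not worse by more than 2 points | 81% to 95% |
| Within ±2 points | 42% to 84% |

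Hand check of the mean shift. Expected change = −(1 − r)·σ·λ, with λ = φ(a)/(1 − Φ(a)) and a = (24.5 − μ)/σ.
- For μ = 23, σ = 5, r = 0.6: a = 0.30, λ = 0.381/0.382 = 1.00, change = −0.4×5×1.00 = −2.0.
- For μ = 27, σ = 4, r = 0.9: a = −0.625, λ = 0.328/0.734 = 0.447, change = −0.1×4×0.447 = −0.18 (simulated −0.19).

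This is regression to the mean from selecting on the score that is then used as baseline.

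**4. What EG versus CG would show.** Both arms pass the same entry threshold and are then randomised, so the shift in step 3 has the same expectation in each and cancels in the difference. If the scale registers only part of a real difference, the observed difference shrinks toward zero. For scale, take 50 EG and 30 CG (80 less the minimum 30 controls), two-sided 5%, 80% power and no dropout, all assumed:

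detectable difference = (1.960 + 0.842)×√(1/50 + 1/30) = 2.802×0.231 = 0.65 SD of change.

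A true difference of 0.65 SD that registered as only 0.3 SD would have about 25% power instead of 80%. How much the scale actually dilutes is unknown.

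**The case against.** The strongest reply is that a fixed anchor, used the same way twice, can still show change. The outcome is a six-item total with room to move both ways, and the sixth item is not tied to school. That stands. A reader might infer that stability is close to guaranteed in both arms; the documents do not support it. Under zero change, the share called stable runs from 42% to 95%, depending on a rule the protocol does not state, and the more predictable artefact is slight apparent improvement rather than no movement. Nor does the figure of about 1% show that the scale cannot respond. It would bear on sensitivity only if perceived decline accrued evenly since youth, which nothing in the protocol says. Evidence of responsiveness may exist in the cited source for the scale; the point here is only that the protocol offers none.

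It is also fair to say that section 3.7 lists EG versus CG first and frames the hypothesis as improvement, that the trial is randomised, that the MoCA is repeated at T2 at the sites marked [IT - SW] in Table 5, and that section 3.1 calls the study a pilot with only a partial evaluation of effectiveness. All of this limits the harm. It does not remove the planned intra-group reading, and the MoCA is not part of the first hypothesis.

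Finally, a direct question about the last six months has weaknesses of its own: it would be unvalidated, would rely on recall in people chosen for memory impairment, and would be open to expectancy because participants know whether they had the robot programme or the booklet. That stands, and it is why such an item should not become the primary or direct measure.

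**Conclusion.** The point holds for the within-EG reading. The primary form never refers to study entry, no rationale for six-month responsiveness is given, stability has no definition, and the selecting score is the baseline. An unchanged or slightly better EG score is what zero effect would often produce: 64–75% not worse and a mean improvement of 0.2–2.0 points, under the assumed mean, SD and retest correlation.

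The randomised comparison survives. Shared insensitivity would tend to mute a real EG–CG difference and cost power, by an amount the documents do not allow one to compute. It would not create a false benefit, and it would be wrong to conclude that the trial is biased towards the system. The change is worth making because it is cheap and settles in advance what the primary outcome can support.

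**What to change.** In sections 3.4, 3.7 and 4.1, make the randomised EG versus CG comparison of MAC-Q change from R to T2 the basis for any conclusion on the primary outcome, and name that comparison in 4.1. Keep the intra-group EG comparison as descriptive. State that stability will not be claimed from an unchanged within-EG MAC-Q alone. This needs only a few sentences and no new data.

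Optionally, add to the T2 form in both arms one item with the same five response options, asking how memory is now compared with study entry. Report it by arm beside the MAC-Q, labelled supportive, not primary and not a direct measure of stability. The MAC-Q stays unchanged for eligibility and outcome.

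The cost of the option is one more question and one more table. Its limits, set out in the objection (no validation, six-month recall, expectancy), should be stated wherever it is reported.
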